5.3.6. Overall Survival (OS)

Definition

OS measured from the date of first dose of study drug to the date of the subject's death from any cause. If the subject is alive or the survival status is unknown, the subject's data will be censored at the date the subject was last known to be alive.

Analysis method

OS will be presented with descriptive summary statistics; Kaplan-Meier method will be used for evaluation, if there are sufficient data.

5.3.7. Patient-reported Outcome (PRO) endpoints

Definition

The patient-reported outcome (PRO) endpoints of interest include domain scales from the EORTC-QLQ-C30 (for subjects ≥ 18 years of age) or Peds FACT-Br (for subjects < 18 years of age), PGIS, PGIC, and EQ-5D-5L (utility value and visual analog scale).

● EORTC QLQ-C30

The EORTC QLQ-C30 version 3.0 is a health-related quality of life instrument that has been widely used in cancer patients. It is composed of both multi-item scales and individual items which include: five functional scales, three symptom scales, a global health status/QoL scale, and six individual items. All of the scales and individual items are transformed to a range of 0 to 100 where a higher scale score represents a higher response level. Notably, a high score for a functional scale represents a high level of functioning and a high score for the global health status/QoL represents a high QoL. In contrast, a high score for a symptom scale/item represents a high level of symptomatology/problems.

Scale scores will be computed, per the developers' scoring manual provided responses are available to at least half of the component items. For all scales, the Raw Score (RS) is the mean of the non-missing component items. For the functional scales, $\text{Score} = 100 \times [1 - (RS - 1)/\text{Range}]$. For the symptom scales/items and the global health status/QoL, $\text{Score} = 100 \times [(RS - 1)/\text{Range}]$. A summary of the scales is given in Table 1 below.

EORTC QLQ-C30 Scales

Scale	Label	# of Items	Item Range	Item Numbers
Global Status/QoL				
Global Status/QoL	Health	QL2	2	6
				29, 30
Functional Scales				
Physical Functioning	PF2	5	3	1 to 5
Role Functioning	RF2	2	3	6, 7
Emotional Functioning	EF	4	3	21 to 24
Cognitive Functioning	CF	2	3	20, 25
Social Functioning	SF	2	3	26, 27
Symptom Scales				
Fatigue	FA	3	3	10, 12, 18
Nausea and Vomiting	NV	2	3	14, 15
Pain	PA	2	3	9, 19
Dyspnoea	DY	1	3	8
Insomnia	SL	1	3	11
Appetite Loss	AP	1	3	13
Constipation	CO	1	3	16
Diarrhoea	DI	1	3	17
Financial Difficulties	FI	1	3	28

● EQ-5D-5L

The EQ-5D-5L is a generic, preference-based instrument for describing and valuing health states in two parts; the EQ-5D descriptive system and the visual analogue scale (VAS). The EQ-5D descriptive system consists of five dimensions: mobility, self-care, usual activities, pain/discomfort and anxiety/depression. Each dimension is scored using a 5-point Likert scale: (1) no problems, (2) slight problems, (3) moderate problems, (4) severe problems, and (5) extreme problems. While the individual numerals have no arithmetic properties, the digits for the 5 dimensions can be combined into a 5 digit number describing the respondent's health state. Janssen will apply the United Kingdom weights to generate patient utilities from the 5 dimensions of the EQ-5D-5L in this study. The VAS records the respondent's self-rated health state on a vertical thermometer with anchors of 0: Worst imaginable health state, and 100: Best imaginable health state.

● Patient Global Impression of Severity

The PGIS is a single-item questionnaire that asks the patient to rate their overall impression of their cancer symptoms. The question text and response options are as follows:

Overall, how would you rate the severity of your cancer symptoms currently?

1. None
2. Mild

3. Moderate

4. Severe

5. Very Severe

● **Patient Global Impression of Change**

The PGIC is a single-item questionnaire that asks the patient to rate their overall impression of the change in their cancer symptoms. The question text and response options are as follows:

Compared to when you received the first treatment in this study, how have your cancer symptoms changed?

1. A lot better now

2. Moderately better now

3. A little better now

4. Neither better, nor worse (no change)

5. A little worse now

6. Moderately worse now

7. A lot worse now

● **FACT-Br**

The Pediatric Functional Assessment of Cancer Therapy – Brain (peds FACT-Br) is available in 2 versions for children and adolescents. It has a recall period of the past 4 weeks. The response scales comprise a 5-point Likert-type scale. Subscale domains address physical well-being, emotional well-being & illness experience, social and family well-being and a brain cancer subscale. Estimated time for completion is approximately 10-15 minutes.

Analysis method

PRO endpoints will be summarized descriptively for the Broad Panel Cohort. Post-hoc or exploratory analyses will be discussed in a separate analysis plan if needed.

Key PRO endpoints:

- EORTC QLQ-C30 global health status/quality of life subscale
- EQ-5D-5L utility score
- EQ-5D-5L VAS

Compliance rates for completion of EORTC QLQ-C30 and EQ-5D-5L at each time point will be generated.

The change from baseline in PRO endpoints at each time point will be summarized with descriptive statistics (N, mean, SD, median, and range [minimum and maximum]). The mean and standard deviation of change from baseline over time will be graphically presented with line plot.

A distribution-based method will be used to define worsening/improvement in EORTC QLQ-C30, i.e., half standard deviation away from the mean score at baseline. Time to worsening and time to improvement will be derived. Time to worsening will be estimated using Kaplan-Meir methods. Death due to disease progression will be considered as worsening. Subjects who have not met the definition of worsening will be censored at the last PRO assessment. Subjects without baseline assessment or post-baseline assessment will be censored at date of treatment start date.

In addition, PGIC and PGIS will be analyzed with descriptive statistics. In addition, change from baseline in PGIS will be summarized with descriptive statistics over time.

Peds FACT-Br (for subjects <18 years of age) will be analyzed for the Pediatric Cohort at the time of final analysis for the Pediatric Cohort.

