To evaluate the efficacy of erdafitinib, in terms of the ORR, as assessed by investigator To evaluate the efficacy of erdafitinib in terms of DOR To evaluate other measures of efficacy including DCR, clinical benefit rate (CBR), PFS, and overall survival (OS)	 The proportion of subjects who achieve a CR or PR based on RECIST v1.1 or RANO as assessed by investigator DOR: the duration from the date of initial documentation of a response to the date of first documented evidence of progressive disease (or relapse for subjects who experience CR during the study) or death, whichever comes first. Data from subjects who are progression-free and alive or have unknown status will be censored at the last tumor assessment DCR: the proportion of subjects with CR, PR or stable disease (SD) CBR: the proportion of subjects with CR, PR or durable SD (defined as a duration of at least 4 months) PFS: the duration from the date of the first dose of study drug until the date of first documented evidence of progressive disease (or relapse for subjects who experience CR during the study) or death, whichever comes first. Data from subjects who are progression-free and alive or have unknown status will be censored at the last tumor assessment OS: measured from the date of first dose of study drug to the date of the subject's death. If the subject is alive or the vital status is unknown, the subject's data will be censored at the
	date the subject was last known to be alive
To evaluate erdafitinib PK To evaluate safety and tolerability of erdafitinib	PK exposure parameters. This endpoint includes pediatrics. Incidence and severity of AEs
To evaluate Health-Related Quality of Life (HRQoL)	Change from baseline in patient-reported health status and physical functioning scales of the European Organisation for Research and Treatment of Cancer Quality-of-life Questionnaire Core 30 (EORTC-QLQ-C30; for subjects ≥18 years of age) or Pediatric Functional Assessment Of Cancer Therapy-Brain (Peds FACT-Br for subjects <18 years of age), Patient Global Impression of Symptom Severity (PGIS), Patient Global Impression of Change (PGIC), and European Quality of Life – 5 Dimensions-5 Levels (EQ-5D-5L).

Objectives	Endpoints
Exploratory	· •
To evaluate the efficacy of erdafitinib in subjects with advanced solid tumors in the Exploratory Cohort in terms of ORR	 The proportion of subjects who achieve a CR or PR based on RECIST v1.1 or RANO as assessed by the investigator DOR, DCR, CBR, PFS, OS

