8.8. Patient-reported Outcomes

Patients' health-related quality of life, symptoms, functioning, and general well-being will be captured using PRO measures (the assessments should be conducted in this order): PGIS, PGIC, EORTC-QLQ-C30 (for subjects \geq 18 years of age) or Peds FACT-Br (for subjects <18 years of age), and EQ-5D-5L utility and VAS. The PRO measures will be electronically collected, according to the Schedule of Activities, to understand change over time in each cohort.

The PGIS is a single question regarding the subject report of disease severity: Considering all aspects of your cancer symptoms right now would you say your cancer symptoms are none, mild, moderate, severe, or very severe? The PGIS is an anchor question that will be used to establish the magnitude of meaningful change in this study.

The PGIC is the PRO counterpart to the Clinical Global Impressions scale, (CGI), which was published in 1976 by the National Institute of Mental Health (US) (eProvide 2019, Guy 1976). It consists of one item taken from the CGI and adapted to the patient.

The EORTC-QLQ-C30 (for subjects \geq 18 years of age) consists of 30 core items, with the 4-point Likert scales ranging from 1: "Not at all" to 4: "Very much" (Michelson 2000, Schwarz 2001). There are 2 items for global health status/quality of life. Functional scales include: Physical functioning (5 items), Role functioning (2 items), Emotional functioning (4 items), Cognitive functioning (2 items), and Social functioning (2 items). Symptom scales/items include Fatigue (3 items), Nausea and vomiting (2 items), Pain (2 items), Dyspnea; Insomnia; Appetite loss; Constipation; Diarrhea; and Financial impact (1 item each). For subjects <18 years of age, the Peds FACT-Br should be used. Peds FACT-Br consists of 4 sets of disease-specific questions pertaining to brain neoplasms (a set of 34 to 37 questions each for child, parent of child, adolescent or parent of adolescent; Peds FACT-Br, 2021).

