9.4.2. Secondary Efficacy Endpoints

- ORR assessed by investigator: the proportion of subjects who achieve a CR or PR based on RECIST v1.1 or RANO as assessed by investigator.
- DOR: the duration from the date of initial documentation of a response to the date of first documented evidence of progressive disease (or relapse for subjects who experience CR during the study), or death, whichever comes first, for subjects. Data from subjects who are progression-free and alive or have unknown status will be censored at the last tumor assessment
- DCR: the proportion of subjects with CR, PR or SD
- CBR: the proportion of subjects with CR, PR or durable SD (defined as a duration of at least 4 months)
- PFS: the duration from the date of the first dose of study drug until the date of first documented evidence of progressive disease (or relapse for subjects who experience CR during the study) or death, whichever comes first, for subjects. Data from subjects who are progression-free and alive or have unknown status will be censored at the last tumor assessment
- OS: measured from the date of first dose of study drug to the date of the subject's death. If the subject is alive or the vital status is unknown, the subject's data will be censored at the date the subject was last known to be alive

Details for the PRO endpoints will be provided in a separate Statistical Analysis Plan.

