5.1.2. Data Handling Rules

Unless specified otherwise, missing values will not be imputed. Other data handling rules if any will be outlined in the DPS.

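### As written, the QLQ-C30 worsening/improvement rule is one group cut-off, not a change from the subject's own baseline; with normal scores about 31% would count as worsened with no change

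*SAP*

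**What the plan says.** SAP 5.3.7 announces a distribution-based method for the QLQ-C30 and spells it out as "half standard deviation away from the mean score at baseline". Time to worsening and time to improvement are derived from this rule, and time to worsening is estimated by Kaplan-Meier. Death due to progression also counts as worsening. The next rule reads: "Subjects without baseline assessment or post-baseline assessment will be censored at date of treatment start date".

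The same section lists the "EORTC QLQ-C30 global health status/quality of life subscale" among the key PRO endpoints. It separately summarises change from baseline in the PRO endpoints at each time point. On the global impression items it says "PGIC and PGIS will be analyzed with descriptive statistics".

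Protocol Section 3 gives the HRQoL endpoint as "Change from baseline in patient-reported health status and physical functioning scales" and names the instruments. Protocol 8.8 adds: "The PGIS is an anchor question that will be used to establish the magnitude of meaningful change in this study". Two deferrals bear on the point. Protocol 9.4.2 says "Details for the PRO endpoints will be provided in a separate Statistical Analysis Plan", and SAP 5.1.2 says "Other data handling rules if any will be outlined in the DPS". Neither of those documents is available here. No other QLQ-C30 threshold appears in the protocol or SAP.

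**The concern.** A subject has one baseline score, so a mean with an SD at baseline can only describe the group. Read that way, the rule draws one line at the group mean minus half an SD (plus half an SD for symptom scales) and compares every later score with it. The subject's own starting point plays no part.

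A subject who starts beyond the line is worsened at the first post-baseline form, due at Cycle 1 Day 14 under the adult schedule in Protocol 1.3, without any change. A subject who starts 1 SD above the mean must fall 1.5 SD to count. The early drop in the Kaplan-Meier curve would then largely show where subjects started, not what happened to them on treatment. Two programmers could also derive different events from the same sentence, depending on whether they follow its words or its likely intent.

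**Working it through.** The documents state no proportion worsened and no baseline QLQ-C30 mean or SD, so there is no figure of the plan's own to reproduce. Normal scores and the between-visit correlation r are assumptions. The half-SD threshold, the score ranges and the item counts come from SAP 5.3.7.

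**1. Share past the cut-off at baseline (literal rule).** P(score ≤ mean − 0.5 SD) = Φ(−0.5) = 0.3085, whatever the mean and SD. The upper tail, which is the worse direction for symptom scales, is the same size. Applied to the roughly 240 Broad Panel subjects, 0.3085 × 240 ≈ 74. This is an upper bound, because adolescents complete a different instrument and not every adult will complete the form.

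Real scores are discrete. With a normal variable rounded to the actual score steps and fitted to assumed baseline means and SDs, the share is:
- global QoL (mean 50–75, SD 18–25): 24–39%
- physical functioning (mean 60–80, SD 18–25): 25–37%

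The two-item scales with 7 score values, and the single items with 4, give much wider ranges that depend heavily on the assumed mean and SD.

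**2. Literal and own-baseline rules at one visit, no mean change.** In baseline SD units, let B be the baseline score, Y the follow-up score and r their correlation. The change Y − B has SD √(2(1 − r)), and its covariance with Y is 1 − r.
- Literal rule flags: Φ(−0.5)
- Own-baseline rule flags: Φ(−0.5/√(2(1 − r)))
- Both flag: the bivariate normal probability that Y ≤ −0.5 and Y − B ≤ −0.5

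| r | Literal | Own baseline | Both | Literal flags with no own fall of 0.5 SD | Own falls missed by the literal rule |
|---|---|---|---|---|---|
| 0.5 | 0.3085 | 0.3085 | 0.1633 | 1 − 0.1633/0.3085 = 47% | 1 − 0.1633/0.3085 = 47% |
| 0.7 | 0.3085 | 0.2593 | 0.1277 | 1 − 0.1277/0.3085 = 59% | 1 − 0.1277/0.2593 = 51% |
| 0.9 | 0.3085 | 0.1318 | 0.0585 | 1 − 0.0585/0.3085 = 81% | 1 − 0.0585/0.1318 = 56% |

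**3. Repeated visits.** The output is time to first worsening, so cumulative flags matter. Simulation with normal scores, equal correlation between all visits, no mean change and no dropout gives the share ever flagged by the fifth visit:

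| r | Literal | Own baseline |
|---|---|---|
| 0.5 | 65% | 65% |
| 0.7 | 56% | 58% |
| 0.9 | 45% | 36% |

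**4. An example.** Assume global QoL has mean 60 and SD 22. The cut-off is 60 − 11 = 49. A subject who rises from 25 to 41.7 is below 49 and counts as worsened. A subject who falls from 83.3 to 50 is above 49 and does not.

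**5. Single items under an own-baseline rule.** A single item has four values, so one step is 100/3 = 33.3 points. For assumed SDs of 18–33, half an SD is 9–16.5 points. Any one-step move therefore meets the threshold.

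**The case against.** The strongest reply is that the intent is plain. Worsening and improvement are words of change, the sentence follows the change-from-baseline paragraph, and SAP 2.5 defines a subject's baseline. A within-subject rule was probably meant. That stands as a reading of intent. It does not remove the problem, because the sentence offers its definition as the meaning of the method and names no own-baseline reference.

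The second reply concerns size. Setting 31% against zero would flatter the correction. Zero applies only to a subject whose score is exactly unchanged; with ordinary noise an own-baseline rule flags 13–31% at one visit, and over repeated visits the totals converge unless r is high. This stands in full.

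Three stronger inferences are tempting, and the documents do not support them.
- **That the rule contradicts the protocol's HRQoL endpoint.** It does not. SAP 5.3.7 still summarises change from baseline, and the time-to-event outputs are additional.
- **That the censoring sentence contradicts the rule.** A fixed cut-off would not need an individual baseline, so the sentence hints at intent. But SAP 5.3.5 uses nearly the same convention for PFS, and requiring a baseline contradicts nothing.
- **That the SAP has dropped the PGIS anchor of Protocol 8.8.** The anchor work may sit in the separate PRO plan named in Protocol 9.4.2, and describing PGIS does not exclude using it as an anchor.

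**Conclusion.** The definition is wrong as written, and it is operative text, not a missing detail. The deferrals to other documents do not withdraw it.

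If scores are normal, about 31% of subjects lie past the worsening cut-off at baseline. The more useful measure is misclassification of individuals. At one visit with no mean change, roughly half to four-fifths of literal flags (47%, 59%, 81% for r = 0.5, 0.7, 0.9) do not reflect an own fall of half an SD, and about half of such falls (47%, 51%, 56%) are missed. These figures rest on normality and the assumed r. A reader should not infer that correcting the rule would remove false worsening; it mainly changes which subjects are flagged.

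The reach is limited to the descriptive QLQ-C30 time-to-worsening and time-to-improvement outputs, including those for global health status/QoL. Change-from-baseline summaries, EQ-5D-5L and the ORR analyses are untouched, and no test or decision rule uses the affected outputs.

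**What to change.** Replace the definition in SAP 5.3.7 with:

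> Worsening (improvement) is a change from the subject's own baseline score of at least 0.5 × the SD of baseline scores in the worse (better) direction: a decrease (increase) for functional and global scales, an increase (decrease) for symptom scales/items.

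Add a note that on the four-level single items any one-step move will meet this threshold at plausible SDs, so those results should be read accordingly.

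Optionally, add a cross-reference to where the PGIS anchor of Protocol 8.8 is applied, for example in the separate PRO plan.

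The cost is one replaced sentence, a note and one derivation. The QLQ-C30 and PGIS data are already collected.

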6. SAFETY

All safety analyses will be based on the safety analysis set, unless otherwise specified.

Safety will be analyzed using the incidence and severity of AEs, physical examinations, vital signs, electrocardiogram (ECG) measurements, clinical safety laboratory assessments, ophthalmologic examinations, performance status and Bone-related Assessments (for adolescents only).

For all continuous safety variables, descriptive statistics will include the N, mean, standard deviation, median, minimum, and maximum. Categorical variables will be summarized using frequency counts and percentages.

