10.2. Appendix 2: Clinical Laboratory Tests

Blood samples for serum chemistry and hematology will be collected according to the Schedule of Activities. More frequent clinical laboratory tests may be performed, as indicated by the overall clinical condition of the subject and for abnormalities that warrant more frequent monitoring.

The investigator must review the laboratory report, document this review, and record any clinically relevant changes occurring during the study in the adverse event section of the eCRF.

The following tests will be performed by the local laboratory:

Hematology Panel

```
-hemoglobin
-platelet count
-white blood cell (WBC) count and absolute neutrophil count (ANC) only
```

Serum Chemistry Panel

-alanine aminotransferase (ALT)	-calcium
-aspartate aminotransferase (AST)	-phosphate
-total bilirubin	-potassium
-chloride	-sodium
-bicarbonate (if feasible)	-magnesium
-creatinine (including calculated	-alkaline phosphatase
creatinine clearance)	-albumin

Possible Hy's Law case reporting requirements are defined in Section 8.4.1

Parathyroid hormone

Thyroid hormones (children and adolescents only)

- Thyroid stimulating hormone (TSH), free thyroxine (T4), and total triiodothyronine (T3)

Insulin-like growth factor 1 (IGF-1) (children and adolescents only)

Creatinine or creatinine clearance will be determined per institutional standard.

A urine or serum sample will be obtained for a pregnancy test (β -hCG) in sexually active female subjects of childbearing potential at screening within 7 days of the first dose, or at Cycle 1 Day 1 prior to the first dose, and at End-of-Treatment. Additional serum or urine pregnancy tests will be performed on Day 1 of every cycle (starting with Cycle 2 Day 1), to establish the absence of pregnancy at any time during the subject's participation in the study.

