Assessment of response will be performed according to Response Evaluation Criteria in Solid Tumors (RECIST, version 1.1) or Response Assessment in Neuro-Oncology (RANO) by the IRC and investigators. Pharmacokinetic assessments (plasma concentrations of erdafitinib and alpha-1-acid glycoproteins, total protein, and fraction unbound, if required, using venous blood samples), biomarker assessments (molecular screening to determine eligibility for the study; and exploratory DNA, RNA, and protein analyses using archival or fresh biopsy tissue and blood (ctDNA) for exploratory research), patients' health-related quality of life (QoL) assessments, and safety assessments (including adverse event [AE] reports and results of vital sign measurements, electrocardiograms [ECGs], physical examinations, clinical laboratory tests, performance status assessment, and ophthalmologic examinations) will be conducted as described on the Schedule of Activities. Additional safety assessments for children and adolescents include radiographic (growth plate assessment and bone age) imaging, DEXA scan for bone densitometry, and clinical laboratory tests for thyroid stimulation hormone (TSH), total triiodothyronine (T3), and free thyroxine (T4) and insulin-like growth factor 1 (IGF-1) will also be conducted as described on the Schedule of Activities in the protocol.

Approximately 280 subjects ≥ 12 years of age with FGFR genetic alterations will be enrolled in the Broad Panel Cohort (approximately 240 subjects for 200 response-evaluable subjects) and Exploratory Cohort (approximately 40 subjects). An additional, approximately 30 subjects will be enrolled in the separate Cholangiocarcinoma Expansion Cohort. The Pediatric Cohort is planned to enroll 20 children or adolescent subjects who had progressed following prior therapies and who had no acceptable standard therapies, and approximately 6 additional children or adolescent subjects who had a newly-diagnosed solid tumor and who had no acceptable standard therapies.

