6.2. Clinical Laboratory Tests

Laboratory data of hematology and serum chemistry up to 30 days after last dose or the end of treatment visit date, whichever is later, will be reported in SI units.

Applicable laboratory results will be graded according to NCI-CTCAE version 5.0.

The following laboratory tests may be analyzed:

- Hematology: hemoglobin, platelet count, WBC count, ANC
- Chemistry: ALT, chloride, albumin, creatinine (including calculated creatinine clearance), alkaline phosphatase, magnesium, AST, bicarbonate, phosphate, blood glucose, potassium, sodium, total bilirubin, total protein, calcium,
- Parathyroid hormone (PTH)
- TSH (adolescents only): Thyroid stimulating hormone, free thyroxine (T4), and total triiodothyronine (T3)
- IGF-1 (adolescents only)

Descriptive statistics will be calculated for each laboratory analyte at baseline and at each scheduled time point. Changes from baseline results will be presented in pre- versus post-intervention cross-tabulations (with classes for below, within, and above normal ranges). Frequency tabulations of the abnormalities will be made. A listing of subjects with any laboratory results outside the reference ranges will be provided. Parameters with predefined NCI-CTCAE toxicity grades will be summarized. Change from baseline to the worst adverse event grade experienced by the subject during the study will be provided as shift tables.

Liver function abnormality by Hy's Law: For subjects with any elevated liver enzyme (AST or ALT) of $>3\times\text{ULN}$, ALP $<2\times\text{ULN}$, and associated with an increase in bilirubin (total) $\geq 2\times\text{ULN}$, a listing for all subjects with all such records will be provided and a summary table of the number of such subjects will be provided.

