6.6. Other Safety Measures

Frequencies of performance score will be reported over time. Descriptive statistics of change in performance scores from baseline will also be provided.

Descriptive statistics for bone-related assessments will be provided at baseline, at each scheduled visit and changes from baseline at each scheduled time point.

Pregnancy testing results will be presented in a by-subject listing.

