7. PHARMACOKINETICS (PK)

Details of population PK analysis, analysis to evaluate relationships between plasma concentration or metrics of systemic exposure and CYP2C9 polymorphism, markers of pharmacological activities (serum phosphate), efficacy or treatment-emergent adverse events may be explored as data allow using population approaches. If relevant, these analyses will be presented in a separate plan and results will be presented in a separate report. All subjects and samples excluded from the analysis will be clearly documented in the separate study report.

Plasma and CSF pharmacokinetic data will be listed for all subjects with available plasma erdafitinib concentrations. Concentration values below the lower limit of quantitation (LLOQ) will be displayed in listings as zero with a flag and handled as zero. Plasma protein binding data such as alpha-1-acid glycoprotein and fraction unbound (unitless) of erdafitinib based on assessment on C2D1 2-4 hour postdose will be listed for all subjects.

For Pediatric Cohort, an interim Bayesian population PK analysis and, if appropriate, NCA analysis of plasma concentration-time data for erdafitinib and markers of pharmacological activities (e.g., serum phosphate) will be performed after 5 children or adolescents (<18 years of age) are enrolled and have completed Cycle 3 Day 1 visit in the study (see protocol Section 9.4.4). In addition, further interim analyses may be conducted after enrollment of additional subjects. Descriptive statistics, including arithmetic and geometric mean, median, standard deviation, coefficient of variation (CV), geometric CV, minimum and maximum, will be tabulated for erdafitinib PK concentrations and protein binding data by time point and age groups (children [6 to <12], adolescents [12 to <15 years of age, 15 to <18 years of age]). PK and protein binding summary table will be performed based on PK analysis set.

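### The SAP labels the bone, thyroid and IGF-1 safety analyses adolescents-only although the protocol performs these tests from age 6; the labels need correcting, and age- and sex-referenced growth summaries would be a cheap improvement

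*SAP*

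**What the plan says.** SAP 6 names the data on which safety will be analyzed and ends the list with "ophthalmologic examinations, performance status and Bone-related Assessments (for adolescents only". SAP 6.2 lists "TSH (adolescents only): Thyroid stimulating hormone, free thyroxine (T4), and total triiodothyronine (T3" and "IGF-1 (adolescents only" among the laboratory tests.

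Protocol 8.3.7 gives the age range for growth-plate radiographs, bone age and DEXA as 6 to under 18 years. Protocol Appendix 2 (10.2) lists "Thyroid hormones (children and adolescents only" and "Insulin-like growth factor 1 (IGF-1) (children and adolescents only". SAP 1.2 agrees with the protocol: "Additional safety assessments for children and adolescents include radiographic (growth plate assessment and bone age) imaging", and it goes on to name DEXA, the thyroid tests and IGF-1. SAP 7 separates the two age groups: "children [6 to <12], adolescents [12 to <15 years of age, 15 to <18 years of age".

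For the bone analysis itself, SAP 6.6 states: "Descriptive statistics for bone-related assessments will be provided at baseline, at each scheduled visit and changes from baseline at each scheduled time point". It gives no age limit and no DEXA metric. Protocol 9.4.7 is equally general.

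On growth, the Schedule of Activities for children and adolescents (Protocol 1.4) and Protocol 8.3.2 ask that height and weight be documented with percentiles. SAP 6.5 handles vital signs and physical examination through adverse events only. Weight appears elsewhere in the SAP only in kilograms, as a demographic variable in Table 4.

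**The concern.** Growth disorder and fracture at ages 6 to under 18 are an adverse event of special interest (Protocol 8.4.7, SAP 6.1.3), on the basis of cartilage findings in animals and a recognized skeletal risk for the drug class (Protocol 2.3 and 8.3.1.1). Adverse event counts need someone to call an abnormality. A gradual shift across the group would show in the quantitative tables instead. If a programmer takes the SAP 6 and 6.2 labels at face value, those tables omit the youngest subjects.

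There is a second, smaller matter. The study is single-arm and these subjects are growing, so an unreferenced change from baseline in weight, height or bone density carries normal growth along with any drug effect. An age and sex reference is the available comparator for normal growth, and the SAP does not call for one.

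**Working it through.** No figure in the plan depends on this point, so the check is a comparison of texts, with one short piece of algebra for DEXA.

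**1. Age scope**

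| Item | SAP 6 or 6.2 label | Protocol scope | Other SAP text |
|---|---|---|---|
| Bone imaging, DEXA | adolescents | 6 to <18 years (8.3.7) | 1.2: children and adolescents; 6.6: no age limit |
| TSH, T3, T4 | adolescents | children and adolescents (Appendix 2) | 1.2: children and adolescents |
| IGF-1 | adolescents | children and adolescents (Appendix 2) | 1.2: children and adolescents |

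Adolescent means 12 to under 18 in SAP 7 and in the title of Protocol 10.7. SAP section 6 also names children and adolescents separately in 6.1.3, 6.2.1 and 6.4, so a literal reading of the labels is possible. For bone, SAP 6 and SAP 6.6 then disagree. For thyroid and IGF-1, no later sentence in SAP 6 widens the label.

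**2. Origin.** Protocol 10.14 records that Amendment 3 lowered the age limit from 12 to 6. The SAP version history says version 4 was written to align with that amendment. Labels that were correct when the youngest subject was 12 appear to have been carried over.

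**3. Percentiles.** Protocol 1.4 has weight percentile documented at treatment-phase examinations. Height percentile is also to be documented, but Protocol 8.3.1.1 names only body weight at subsequent visits, so the timing of height is less certain. No SAP section specifies a percentile table or listing.

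**4. DEXA.** Let g > 0 be the normal rate of gain in density, t the time on treatment, and d (0 < d < 1) the fraction of normal gain removed by the drug.

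- Raw change = (1 − d)·g·t, which is positive.
- Z-score change = −d·g·t / SD, which is negative.

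The raw mean can therefore rise while subjects fall behind their peers. The documents give no value for d, so this shows the direction only.

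**5. Precision.** The planned number under 18 is 20 + about 6 = about 26. Assume an SD of Z-score change of 0.3 to 0.5 (not in the documents) and, at best, paired scans in all 26. With t(25, 0.975) = 2.06, the 95% half-width is 2.06 × 0.3/√26 = 0.12 to 2.06 × 0.5/√26 = 0.20. Such tables can only be descriptive.

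**The case against.** The best defense is that the rest of the SAP shows what is meant. SAP 6 bases safety analyses on the safety set, and SAP 2.2.2 puts the whole Pediatric Cohort in it. SAP 6.6 has no age limit. SAP Table 5 applies the word adolescents from age 6 when describing the Lansky score. The labels in 6.2 sit in a permissive list of tests, and the sentence that follows covers each analyte. SAP 6 also promises generic statistics for all continuous safety variables, which could take in weight and height. The protocol mentions percentile curves as a clinical prompt, not as an endpoint, and nothing says DEXA will be reported in raw form only.

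Most of this stands, and it rules out several stronger readings that a reader might infer:

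- That children aged 6 to under 12 were deliberately excluded. The safety set, SAP 1.2 and SAP 6.6 all point the other way.
- That a given number of assessments per child will be lost. Any such count holds only under the literal reading, and the number of subjects in that age band is not stated.
- That growth summaries are barred. They are only unspecified.
- That the unnamed DEXA metric is an error. It is missing detail.
- That growth toxicity in young children would go unrecorded. Imaging abnormalities must be reported as adverse events (Protocol 8.3.7), and the special-interest category starts at age 6.

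The defense explains the labels without correcting them. Two sections still give the wrong scope, and for thyroid and IGF-1 the reader must infer the right one.

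**Conclusion.** The three labels are wrong as written and conflict with the protocol and with SAP 1.2. Leftover wording is the likely cause; that is an inference from the amendment history. Age- and sex-referenced growth and DEXA summaries are an improvement and not the repair of an error. A reference removes expected growth but not the effects of disease or earlier treatment.

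The severity is minor. The reach is limited to descriptive safety tables for about 26 planned pediatric subjects. No size of drug effect and no number of lost results is claimed. Counting of adverse events of special interest is unchanged, and so is inference on overall response rate.

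**What to change.** **Correct:** in SAP 6 and in both places in SAP 6.2, replace the adolescents-only label with children and adolescents aged 6 to under 18 years. This is a text edit with no other cost.

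**Improve, for subjects under 18:** in SAP 6.5 or 6.6, add a descriptive summary or by-subject listing of change from baseline in weight percentile or SD score, and in height percentile where recorded. Report DEXA change as an age- and sex-specific Z-score with the reference set named. The protocol already calls for the percentiles and scans. The cost is choosing a growth chart and a DEXA reference, possibly deriving some Z-scores, and programming a few outputs. With so few subjects, a listing may serve as well as a table. Listings of bone age against chronological age, Tanner stage or growth-plate status are optional.
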